4.2.2. Treatment Period

- The Treatment Period will begin with the Baseline visit on Day 1. Study visits will also occur at Week 4, Week 8, Week 12, and Week 16.

- At the Baseline visit, eligible subjects will be randomized in a 1:1 ratio to receive either mepolizumab 100 mg SC or placebo SC.
- Study treatment will be prepared by a designated, qualified, unblinded member of the site staff who is independent of the protocol-defined study assessments (See Section 6.1).
- Study treatment will be administered by SC injection at the Baseline visit, Week 4, Week 8, and Week 12 (last dose). Each SC injection will be administered by a trained member of the site staff who is blinded to study treatment. See Section 6.1.1 for injection site instructions and study treatment administration details.
- Subjects will remain in the clinic for safety monitoring one hour after each administration of study treatment. Subjects will be observed for adverse events (AEs) including systemic reactions (i.e., allergic (type I hypersensitivity) reaction and other systemic reaction) and local injection site reactions (See Section 6.1.2).
- There are no planned dose adjustments during the study.
- The last dose of study treatment will be administered at Week 12. Study treatment will **not** be administered at Week 16. For those subjects randomized to mepolizumab, four doses will provide therapeutic coverage to Week 16 when efficacy assessments for the primary endpoint will occur. For this reason, the Week 16 visit is considered to be part of the Treatment Period while also serving as the first follow-up visit (Post-Treatment Visit 1).
- Subjects will continue to apply the same non-prescription, non-medicated (without an active ingredient) emollient twice daily. On study visit days, the subject must not apply the emollient within the 2-hour period preceding the study visit. See Section 6.10.1 for further details regarding emollient use.
- Subjects who prematurely discontinue study treatment will be followed for 8 weeks after the last dose and will be scheduled for the following visits (Section 5.4 and Table 3):
 - Early Withdrawal Visit (if the decision is made to prematurely discontinue study treatment <4 weeks after last dose of study treatment),
 - Post-Treatment Visit 1 (4 weeks after last dose of study treatment), and
 - Post-Treatment Visit 2 (8 weeks after last dose of study treatment).

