5.4.1. Early Withdrawal from Study Treatment

Subjects must **permanently discontinue study treatment** for any of the following reasons:

- Subject presents with worsening AD or any other condition that requires treatment with a prohibited medication.
- Subject experiences an adverse event(s) which is considered to be related to study treatment or study procedures and, in the investigator's judgment, is severe enough in nature to warrant treatment discontinuation.
- Subject experiences a cardiovascular or hematologic AE consistent with specific Common Terminology Criteria for AEs (CTCAE) version 4.02 Grade 2 (moderate) or higher (See SRM).
- The subject's randomized treatment assignment is unblinded by the investigator or treating physician.
- Subject becomes pregnant.
- Sponsor request (after discussion with the investigator), for reasons such as a significant protocol deviations or subject noncompliance.
- Study is terminated by the sponsor.
- Subject meets liver chemistry stopping criteria (See Section 5.4.4).
- Subject meets QTcF stopping criteria (See Section 5.4.5).

Subjects who permanently discontinue study treatment will be followed for 8 weeks after the last dose of study treatment. Every effort will be made by the investigator to encourage the subject to remain in the study to complete the two Post-Treatment visits providing that consent has not been withdrawn for subsequent visits.

If the decision is made to permanently discontinue study treatment less than 4 weeks after the last dose, an Early Withdrawal Visit will be scheduled as soon as is reasonably possible. Post-Treatment Visit 1 will then be scheduled 4 weeks after the last dose of study treatment, and Post-Treatment Visit 2 will be scheduled 8 weeks after the last dose of study treatment.

If the decision is made to permanently discontinue study treatment at a scheduled visit and approximately 4 weeks have elapsed since the last dose of study treatment, the procedures of Post-Treatment Visit 1 will be performed. Post-Treatment Visit 2 will be scheduled 8 weeks following the last dose of study treatment.

The investigator will record the primary reason for permanent discontinuation of study treatment and subsequent study withdrawal in the electronic Case Report Form (eCRF).

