9.4.2. Secondary Analyses

The secondary efficacy endpoints are defined in Section 3.

IGA: Subjects' change from baseline in IGA score and the proportion of subjects with a 2-point decrease from baseline will be summarized by visit. Point-estimates and 90% confidence intervals for the differences between the experimental and vehicle arm at Week 16 will be presented. No formal hypothesis testing will be performed.

EASI: Subject's change from baseline/percent change from baseline will be summarized by visit. Point-estimates and 90% confidence intervals for the differences between the experimental and vehicle arm at Week 16 will be presented. No formal hypothesis testing will be performed.

Continuous endpoints will be presented as means and 90% confidence intervals.

Safety Analyses

AEs will be coded using the MedDRA coding dictionary and summarized by preferred term and treatment group. SAEs occurring pre-treatment and AEs and SAEs occurring during active treatment and post-treatment will be summarized separately. Separate summaries will be provided for all AEs, investigational product-related AEs, SAEs, AEs of special interest (including systemic reactions [allergic/type I hypersensitivity or Systemic Other] and local injection site reactions) and for AEs leading to permanent discontinuation of investigational product or withdrawal from the study. All laboratory parameters for clinical chemistry and hematology will be summarized and tabulated.

Summary statistics of pulse rate and systolic and diastolic blood pressure will be presented by visit.

Immunogenicity will be summarized using appropriate descriptive statistics.

Full details of planned analyses of safety endpoints will be included in the RAP.

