12.2. Appendix 2: Assessment Windows

Clinic visits are scheduled to take place as specified in the protocol. Unscheduled visit will be excluded from analyses on any population. For all clinic visits, nominal visit days and times will be used for reporting; for example, if a subject recorded value on the Week 4 visit that were made on Week 3 of treatment, they will be presented as Week 4 values.

If a subject withdraws at a scheduled visit, and these data were scheduled to be collected at that visit, the data will be summarised and analysed (as appropriate) together with data from subjects who did not withdraw. If a subject withdraws at a scheduled visit at which these data were not scheduled to be collected, or if a subject withdraws between scheduled visits, data will be slotted to the next visit where the data was scheduled to be collected according to the study flowchart. The protocol visits windows of ± 3 days should be applied to the assignment of withdrawal visits, so that if a subject withdraws within the appropriate number of days from the last visit where that data was scheduled to be collected, they would get that data slotted to that visit and otherwise the data will be slotted to the next scheduled visit.

The early withdrawal visit will then be re-labelled as the corresponding visit. The same approach will be followed to Post Treatment 1 and Post Treatment 2 visits.

If there is more than one assessment associated with a particular visit interval, then the latest assessment will be used for summary tables and analyses. Where two or more findings (e.g. ECG (i.e. site interpretations will be used), laboratory data) slot to the same visit interval, the most 'abnormal' results will be used, i.e. according to the following hierarchy: Abnormal-Clinically Significant > Abnormal – not clinically significant > Normal.

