12.5.3. Efficacy

Efficacy
Investigators Global Assessment (IGA)

CCI - This section contained Clinical Outcome Assessment data collection questionnaires or indices, which are protected by third party copyright laws and therefore have been excluded.

 A Responder is defined as a subject who has an IGA score of 0 or 1 and a minimum 2-grade improvement from baseline. This is calculated for each study visit. As per protocol, a non-responder imputation will be used for all early withdrawal subjects where

Efficacy

subject's data will be imputed as a Non-Responder for all post withdrawal visits. This imputation will be used for summary and analysis table for primary and secondary endpoints.

- The observed IGA score classifications will be used for each visit. For all early withdrawal subjects the data from Post-Treatment 1/Post-Treatment 2/Early Withdrawal visits will be slotted using the algorithm detailed in Section 12.2
- AD flare/relapse for IGA is defined as IGA score of 3 or 4 after achieving an IGA score of 0 or 1 and at least a 2- grade improvement from the baseline.

Body Surface Area

Body Region	% Involvement (0-100% each area)	% Involvement x Proportionality Multiplier	Regional % BSA Involvement
Head and neck		___ x 0.1	
Upper extremities		___ x 0.2	
Trunk		___ x 0.3	
Lower extremities		___ x 0.4	
Total Involved % BSA (sum of the 4 area values) =			_____

EASI

CCI - This section contained Clinical Outcome Assessment data collection questionnaires or indices, which are protected by third party copyright laws and therefore have been excluded.

- The observed EASI data will be used for each visit. For all early withdrawal subjects, data from Post-Treatment 1/Post-Treatment 2/ Early Withdrawal visits will be slotted using the algorithm detailed in Section 12.2.
- AD flare/relapse for EASI is defined as increase in EASI score of ≥25% from Baseline.

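### Subjects who stop treatment after the Day 1 or Week 4 dose have no planned Week 16 visit, so the Week 16 EASI summaries leave them out

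*Protocol*

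**What the plan says.** Doses are given on Day 1 and at Weeks 4, 8 and 12 (Protocol 4.2.2). For a subject who stops early, Protocol 5.4.1 states: "Subjects who permanently discontinue study treatment will be followed for 8 weeks after the last dose of study treatment". The last of these visits is fixed in the same section: "Post-Treatment Visit 2 will be scheduled 8 weeks following the last dose of study treatment". Table 3 plans nothing later. The first listed reason for mandatory discontinuation is "Subject presents with worsening AD or any other condition that requires treatment with a prohibited medication".

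For EASI, a secondary endpoint, Protocol 9.4.2 promises a comparison at a fixed time: "Point-estimates and 90% confidence intervals for the differences between the experimental and vehicle arm at Week 16 will be presented". SAP 12.5.3 sets the data rule: "The observed EASI data will be used for each visit". SAP 7.2.3 plans no strategy for intercurrent events, and SAP 7.2.5.1 plans no statistical analysis of the secondary endpoints.

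IGA is handled differently. Protocol 9.4.1 counts subjects who leave the study before Week 16 as non-responders, and SAP 12.5.3 applies this to all early withdrawals. In the SAP's list of efficacy tables, the non-responder note appears on Tables 2.1 and 2.3 (IGA response) but not on Tables 2.4 to 2.6 (EASI).

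**The concern.** Follow-up is tied to the last dose, while the endpoint is tied to Week 16. For the first two doses the two do not meet. The resulting loss is built into the schedule. It falls on subjects who still consent to visits, and so differs from ordinary drop-out.

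A subject who stops because AD has worsened probably has a poorer EASI than one who continues. Leaving such subjects out makes the Week 16 mean in their arm look better than the mean over everyone treated. If the two arms lose different numbers, or if completers respond differently in the two arms, the between-arm difference shifts as well. The same applies to the EASI 50/75 proportions, for which the SAP's Table 2.6 shell still shows a between-arm difference with a 90% interval.

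**Working it through.** **Planned numbers.** Protocol 4.3 gives 50 evaluable subjects and 10% drop-out: 50 / 0.9 = 55.6, rounded up to 56, which matches the stated 56. Planned drop-out is thus 56 − 50 = 6 subjects, or about 3 per arm of 28.

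**Visit timing.** Post-Treatment Visits 1 and 2 fall at the week of the last dose + 4 and + 8.

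| Last dose | Visit 1 | Visit 2 | Week 16 visit planned? |
|---|---|---|---|
| Day 1 | Week 4 | Week 8 | no |
| Week 4 | Week 8 | Week 12 | no |
| Week 8 | Week 12 | Week 16 | yes |
| Week 12 | Week 16 | Week 20 | yes |

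**Visit slotting.** SAP Appendix 2 keeps a withdrawal assessment at the preceding visit if it lies within 3 days; otherwise "data will be slotted to the next visit where the data was scheduled to be collected according to the study flowchart". It adds: "The same approach will be followed to Post Treatment 1 and Post Treatment 2 visits". With visits on time, the last EASI slots to Week 8 or Week 12. If the Week 4 dose was postponed by the 2 weeks that Protocol 5.4.3 allows, Visit 2 falls at Week 14 and is relabelled Week 16. It would then be counted at Week 16 without having been measured then.

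**How many.** The documents do not split stops by dose. If k of the 6 planned drop-outs stop after the Day 1 or Week 4 dose, k runs from 0 to 6. Week 16 EASI then lacks k / 56 of subjects by design, from 0% to 6 / 56 = 10.7%.

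**Effect on the EASI means.** Let f be the fraction missing in an arm and m the completers' mean percent change. Assume stoppers would have had 0% change at Week 16. The all-subject mean is (1 − f) × m, so the observed mean overstates improvement by f × |m|. The shift in the between-arm difference is the placebo overstatement minus the mepolizumab overstatement. All inputs below are assumed.

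| Missing, placebo / mepolizumab | Completer mean, placebo / mepolizumab | Overstatement, placebo / mepolizumab | Effect on the difference |
|---|---|---|---|
| 3/28, 1/28 | −35%, −35% | 3.75, 1.25 | understated by 2.5 points |
| 3/28, 1/28 | −35%, −60% | 3.75, 2.14 | understated by 1.6 points |
| 3/28, 3/28 | −35%, −35% | 3.75, 3.75 | none |
| 3/28, 3/28 | −35%, −60% | 3.75, 6.43 | overstated by 2.7 points |

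The last two rows use up all 6 planned drop-outs.

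**Scale.** With 25 per arm and an assumed SD of 30 to 50 points, the 90% half-width is about 1.677 × SD × √(2/25), or 14 to 24 points.

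**The case against.** The strongest objection is that the extra visit may not measure what is missing. Protocol 6.10.2 allows prohibited medication for worsening AD after early withdrawal from treatment. A Week 16 EASI in these subjects may therefore be a value on other therapy, as good as a completer's or better. Collecting it without a rule would not remove the bias. It could also disturb the primary endpoint: a subject who stops treatment but attends Week 16 has not left the study in the sense of Protocol 9.4.1, so a clear score after other treatment might be counted as success.

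This stands as a reason to add an analysis rule, but it does not justify leaving the gap. The plan already takes Week 16 EASI as observed, possibly after other therapy, from subjects who stop after the Week 8 dose. Those who stop one dose earlier for the same reason are absent.

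The objection that the effect is small and EASI only secondary also has force. No hypothesis is tested, early stoppers contribute to earlier visits, and the SAP's Table 2.4 shell shows arm summaries without a difference. Protocol 9.4.3 foresaw an exploratory repeated-measures model for EASI, if data permitted, that could have used the earlier visits, but the SAP does not carry it forward. The arm means and the Table 2.6 differences still rest on the restricted set.

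Three stronger readings are tempting, and the documents support none of them:

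- A reader might infer that placebo loses more subjects and that the bias therefore works against mepolizumab. Nothing in the documents says which arm loses more, and with equal losses and a larger mepolizumab response the sign reverses.
- A reader might infer that only subjects still on treatment are compared. Stops after the Week 8 or Week 12 dose do have a Week 16 visit.
- A reader might infer that the primary result or the futility decision is undermined. Early withdrawals count as IGA non-responders, and the interim (SAP 3.1) used IGA response at Week 8. The protection is called large rather than complete because footnotes to the Table 2.1 and 2.3 shells confine it to withdrawal for lack of efficacy or disease progression.

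**Conclusion.** The gap is real and follows directly from the schedule: consenting subjects whose last dose was Day 1 or Week 4 have no planned Week 16 assessment, and the Week 16 EASI summaries omit them. Since worsening AD is a reason to stop, those values are likely to be informative.

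The direction and size of the bias in the between-arm difference cannot be determined from the documents. On the assumed values, the difference is understated by 1.6 to 2.5 points, unchanged, or overstated by 2.7 points, while single-arm means are flattered by 1.25 to 6.4 points. These figures rest on 0% change in stoppers, the stated completer means, and one to three early stoppers per arm. The shift is small against the likely interval width and concerns a secondary, descriptive endpoint. It is worth correcting because the remedy is cheap and the plan treats the same event differently according to which dose came last. The SAP records that the study was terminated for futility, so this is a criticism of the plan and does not challenge that decision.

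**What to change.** - **Protocol 5.4.1 and Table 3:** add a Week 16 assessment visit (IGA, EASI, adverse events, concomitant medication) for subjects whose last dose was Day 1 or Week 4 and who have not withdrawn consent. Later stops already have one.
- **Protocol 9.4.1 and SAP 12.5.3:** state that a subject who stopped treatment early, or used prohibited medication for AD before Week 16, remains a non-responder for IGA and for EASI 50/75 whatever score is observed.
- **Week 16 EASI change:** report it twice, once with all observed values and once with values after prohibited medication flagged or excluded.

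The cost is one extra visit for a few subjects, using assessments that sites already perform, and a little more analysis. The visit recovers nothing from subjects who withdraw consent or are lost to follow-up.

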5.4.2. Early Withdrawal from Study

The subject must **discontinue study treatment and be withdrawn from the study** for the following reasons:

- Subject demonstrates significant noncompliance with the study procedures. (See the SRM for examples.)
- Subject is lost to follow-up.
- Subject withdraws consent to participate in the study. If specified by the subject, the investigator should document the reason for withdrawal of consent.
- Study is terminated by the sponsor.
- Sponsor request (after discussion with the investigator) for reasons such as a significant protocol deviations or subject noncompliance.

Subjects who are **withdrawn from the study** will be asked to return to the clinic for an Early Withdrawal Visit providing that consent has not been withdrawn for subsequent visits.

If a subject withdraws from the study, he/she may request destruction of any samples taken, and the investigator must document this in the site study records. The investigator will record the primary reason for study withdrawal in the eCRF.

The following actions must be taken in relation to a subject who fails to attend the clinic for a required study visit:

- The site must attempt to contact the subject and re-schedule the missed visit as soon as possible.
- The site must counsel the subject on the importance of maintaining the assigned visit schedule and ascertain whether or not the subject wishes to and/or should continue in the study.
- In cases where the subject is deemed 'lost to follow up', the investigator or designee must make every effort to regain contact with the subject (where

possible, 3 telephone calls and if necessary a certified letter to the subject’s last known mailing address or local equivalent methods). These contact attempts should be documented in the subject’s medical record.

- Should the subject continue to be unreachable, only then will he/she be considered to have withdrawn from the study with a primary reason of “Lost to Follow-up”.

5.4.3. Postponement of Study Treatment

Administration of study dose and scheduled study visit assessments will be postponed during treatment for acute infection with oral or IV non-cytotoxic antibiotics, antivirals, anti-protozoals or antifungals. Upon completion of treatment of the acute infection, the postponed dose of study drug will be administered as soon as feasible but not further than 2 weeks from the originally planned visit schedule.

[figure not shown]
Successive administrations of study dose (if applicable) will resume as per the subject’s originally planned visit schedule. If dose cannot be administered within 2 weeks from the original schedule, subjects must be discontinued from study treatment.

5.4.4. Liver Chemistry Stopping Criteria

Liver chemistry stopping and increased monitoring criteria have been designed to assure subject safety and evaluate liver event etiology (in alignment with the FDA premarketing clinical liver safety guidance).

[figure not shown]
<http://www.fda.gov/downloads/Drugs/GuidanceComplianceRegulatoryInformation/Guidances/UCM174090.pdf>

Figure 3 Liver Chemistry Stopping and Increased Monitoring Algorithm

Liver Safety Required Actions and Follow up Assessments Section can be found in [Appendix 8](#).

Figure 4 Liver Chemistry Increased Monitoring Algorithm with Continued Therapy for ALT $\geq 3xULN$ but $< 8xULN$

Required Actions and Follow up Assessments for all subjects who meet liver chemistry stopping or increased monitoring criteria can be found in [Appendix 8](#).

5.4.4.1. Study Treatment Restart or Rechallenge

Study treatment restart or rechallenge after liver chemistry stopping criteria are met by any subject participating in this study is not allowed.

5.4.5. QTcF Stopping Criteria

- The *same* QT correction formula *must* be used for *each individual subject* to determine eligibility for and discontinuation from the study. Note: QTcF will be utilized for this study. This formula may not be changed or substituted once the subject has been enrolled.
- The QTcF should be based on averaged QTcF values of triplicate electrocardiograms obtained over a brief (e.g., 5-10 minute) recording period.

A subject who meets either of the bulleted criteria below will be withdrawn from the study:

- QTcF >500 msec OR Uncorrected QT >600 msec
- Change from baseline of QTcF >60 msec

For patients with underlying **bundle branch block**, the discontinuation criteria listed below apply:

Baseline QTcF with Bundle Branch Block	Discontinuation QTcF with Bundle Branch Block
<450 msec	>500 msec
450 – 480 msec	≥530 msec

Note: Unscheduled ECGs may be performed as clinically indicated during the study.

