- Subjects who are withdrawn from the study will complete an Early Withdrawal visit and then exit the study. See Section 5.4 and Table 3.

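### Protocol 5.4.5 withdraws a subject who meets the QTcF limits from the study, while 5.4.1 stops only treatment and keeps the subject in follow-up for 8 weeks after the last dose

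*Protocol*

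**What the plan says.** **Protocol 5.4.5.** The limits are QTcF above 500 msec or uncorrected QT above 600 msec, or a QTcF rise of more than 60 msec from baseline. A separate table gives limits for bundle branch block. The action is: "A subject who meets either of the bulleted criteria below will be withdrawn from the study". The first bullet of the section uses the same language, applying one correction formula "to determine eligibility for and discontinuation from the study".

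**Protocol 5.4.1**, the list of reasons to stop study treatment, includes "Subject meets QTcF stopping criteria (See Section 5.4.5"). It then states: "Subjects who permanently discontinue study treatment will be followed for 8 weeks after the last dose of study treatment". If about 4 weeks have passed since the last dose when the decision is made at a scheduled visit, "the procedures of Post-Treatment Visit 1 will be performed. Post-Treatment Visit 2 will be scheduled 8 weeks following the last dose".

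**Protocol 5.4.2**, the list of reasons to leave the study, does not contain QTcF. Subjects on that route "will be asked to return to the clinic for an Early Withdrawal Visit providing that consent has not been withdrawn for subsequent visits". Section 4.2.2 is explicit about what follows: "Subjects who are withdrawn from the study will complete an Early Withdrawal visit and then exit the study".

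**Schedule.** Post-baseline ECGs fall at Week 4 (pre-dose), Week 16 and Early Withdrawal (Protocol 7.1, Table 3), and unscheduled ECGs are allowed. On dosing, 4.2.2 says: "The last dose of study treatment will be administered at Week 12".

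**The concern.** A site that meets the event finds two instructions. One section ends participation after a single visit. The other requires 8 weeks of follow-up from the last dose and asks the investigator to encourage the subject to stay. Two sites could each comply with the protocol and handle the same QTc event differently.

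The stake is safety follow-up. If 5.4.5 is followed, a subject with a possible cardiac signal stops being seen on schedule after the exit visit. From then on the investigator need not actively look for new adverse events in a former subject (7.4.1.1).

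**Working it through.** The plan gives no figure to reproduce. The check sets the sections side by side and then counts days on the visit schedule.

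**Step 1. Is there a text that reconciles the two?**

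| Place in Protocol | Treatment of the QTcF event |
|---|---|
| 5.4.5, action sentence | Withdrawal from the study |
| 5.4.5, first bullet | Discontinuation from the study |
| 5.4.1 | Treatment stop, citing 5.4.5, with follow-up |
| 5.4.2 | Not listed |
| 7.4.5 | Refers only to withdrawal criteria in 5.4.5 |

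Dual listing does not explain it. Sponsor request and study termination appear in both 5.4.1 and 5.4.2; QTcF appears only in 5.4.1. The nearest comparable rules are treatment stops: a cardiovascular AE of Grade 2 or higher (5.4.1), and a liver stopping event, after which the subject may stay for follow-up (Appendix 8).

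**Step 2. What does the exit visit keep?** Table 3 marks the Early Withdrawal visit for ECG, physical examination, vital signs, haematology, chemistry, PK, immunogenicity and IL-5. Each of these is therefore collected at exit. What disappears is what comes later.

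**Step 3. How much scheduled follow-up is lost?** Count days from the last dose. Post-Treatment Visit 1 is day 28 and Post-Treatment Visit 2 is day 56. Visit windows are ±3 days (Table 3).

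*Trigger at Week 4.* The last dose was Day 1, assuming the pre-dose ECG is acted on before the injection. Under 5.4.1 the subject has Post-Treatment Visit 1 procedures at once and Post-Treatment Visit 2 later (two visits). Under 5.4.5 there is one visit.
- Lost: 56 − 28 = 28 days.
- Shortest with windows: (56 − 3) − (28 + 3) = 22 days.
- Longest with windows: (56 + 3) − (28 − 3) = 34 days.
- Scheduled ECGs lost: none, because Post-Treatment Visit 2 has no ECG.

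*Trigger at Week 16.* The last dose was Week 12, so Week 16 is day 28 and Week 20 is day 56. The same 28 days (22 to 34) are lost. No dose remains to stop, so the only effect of 5.4.5 is to cancel Week 20.

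*Trigger less than 4 weeks after a dose* (an unscheduled ECG). Under 5.4.1 there are three visits: Early Withdrawal, Post-Treatment 1 and Post-Treatment 2. Under 5.4.5 there is one. With the Early Withdrawal visit on day *e*, follow-up lost = 56 − *e*. The part inside the SAP on-treatment window (last dose + 28 days, SAP 12.3.1) = 28 − *e*. The values of *e* below are illustrative.

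| *e* | Days lost | Of which on-treatment |
|---|---|---|
| 7 | 49 | 21 |
| 14 | 42 | 14 |
| 21 | 35 | 7 |

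One scheduled ECG, at Post-Treatment Visit 1, is also lost.

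**The case against.** The strongest reply is that the documents already favour one reading. Section 5.4.1 names the event and gives the action, 5.4.2 leaves it out, and 5.4.5 is headed as stopping criteria and calls its bundle branch block limits discontinuation criteria. On that view 5.4.5 contains a wording slip, not an open design question. This stands as a guide to intent and is why the fix follows 5.4.1. It does not remove the conflict: the sentence in 5.4.5 is operative, and no rule of precedence tells a site to disregard it.

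The second reply is that little is lost. This stands in large part. SAEs, AEs of special interest and AEs that led to stopping treatment are followed until they resolve or stabilise (7.4.1.3). An ECG abnormality judged clinically significant is itself an AE (Appendix 11). An SAE learned of after exit and thought related must still be reported (7.4.1.1). What remains is the active, scheduled search for new events. The losses of 35 to 49 days need an unscheduled ECG.

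A reader might also infer more than the text supports:

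- *That the subject leaves without PK, immunogenicity or a physical examination.* Table 3 marks all three at Early Withdrawal; only the later repeat is lost.
- *That Week 16 is the plainest clash.* By 5.5 a subject with all doses and a completed Week 16 visit has completed study treatment, so 5.4.1 has nothing left to stop. The head-on conflict is during dosing.
- *That the primary endpoint is affected.* Any such effect would be rare and would turn on how the slotting and imputation text in SAP 12.2 and 12.5.3 is read. The documents do not establish one.

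**Conclusion.** The inconsistency is real, and 5.4.5 is wrong as written. Its size is modest and concerns safety follow-up only. A Week 4 or Week 16 trigger costs one visit and about 28 days (22 to 34), with no scheduled ECG lost. A trigger less than 4 weeks after a dose costs two visits and one scheduled ECG.

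These sizes assume that the site follows 5.4.5 over 5.4.1. The Week 4 figure also assumes that the pre-dose ECG is acted on before the injection; if the dose has been given, the third case applies. The documents give no rate at which subjects would meet the limits, so no expected number of affected subjects is stated.

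The SAP Introduction records that the study was later stopped for futility. That does not reconcile the text under which subjects were enrolled.

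**What to change.** In Protocol 5.4.5, replace the action sentence with:

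> *A subject who meets either of the limits listed below, or the bundle branch block limits in the table, will permanently discontinue study treatment (if any doses remain) and attend the follow-up visits of Section 5.4.1, ending 8 weeks after the last dose. A subject who meets a limit at Week 16 will continue to the Week 20 visit.*

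The bundle branch block limits must be named, because the current sentence covers only the bulleted criteria. Week 16 must be named, because 5.4.1 alone has no treatment to stop there.

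In the first bullet of 5.4.5, change the end of "to determine eligibility for and discontinuation from the study" so that the formula governs eligibility for the study and discontinuation of study treatment. In 7.4.5, refer to QTcF treatment stopping criteria.

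If the sponsor does intend exit, the alternative is to move QTcF from 5.4.1 to 5.4.2 with a stated reason. That would be consistent, but it would give up the follow-up and depart from the liver and cardiovascular AE rules.

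The cost is three wording edits and, for each affected subject, one or two visits that the protocol already defines. No procedure is added.
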